#### 2.7.1.1 Adverse events of special interest / grouping of AEs

Adverse event of special interest (AESI): The number and percentage of participants who reported TEAEs of special interest will be summarized by PT, treatment group. PTs will be sorted in descending order of frequency in the total column. If a participant reported more than one adverse event with the same PT, the AE will be counted only once. If a participant reported more than one AE within the same AESI, the participant will be counted only once at that AESI. Listing of participants with adverse event of special interest will be provided.

The Compound Case Retrieval Strategy (CRS) will be used to determine the MedDRA search criteria to be used to identify events of special interest.

Adverse event of special interest will include the following:

- Hepatotoxicity (Hepatic events)
- New onset or worsening of diabetis mellitus

For search criteria of AE of special interest, refer to Appendix 5.3.

| Novartis | Confidential | Page 24 of 37           |
|----------|--------------|-------------------------|
| SAP      |              | Study No. CKJX839A1GB01 |

The most recent list of adverse events of special interest at the time of database lock will be used. CRS listing will be provided.

### 2.7.2 Deaths

Please refer section 2.7.1.

## 2.7.3 Laboratory data

There are no regular laboratory tests required by this protocol. All blood tests will be performed locally by clinical pathology laboratories, in common with usual practice. Methods for sampling, handling and analysis will be the same as usually applied in routine care.

Abnormal laboratory findings, that are detected during the study or are present at baseline and significantly worsen following study drug administration, and are deemed as clinically significant by the investigator will be recorded as AEs if they lead to treatment discontinuation.

### 2.7.4 Other safety data

### 2.7.4.1 Vital signs

Absolute values, change from baseline and percentage change from baseline will be summarized for vital sign parameters by visit, time point and treatment group using overall data. Baseline and change from baseline in height, will be summarized by visit, treatment group using overall data.

All vital signs data will be listed by treatment group, participant, and visit/time and if ranges are available, abnormalities will be flagged.

## 2.8 Patient-reported outcomes

#### 2.8.1 The CSQ-8 PROMs Questionnaire

The details about Client Satisfaction Questionnaire (CSQ) and the endpoints were mentioned in section 2.6.1.1. For more details on the questionnaire, please refer to the study protocol.

#### 2.8.2 The PAM PROMs Questionnaire

The details about Patient Activation Measure (PAM) Questionnaire and the endpoints were mentioned in section 2.6.1.2. For more details on the questionnaire, please refer to the study protocol.

#### 2.10.1 Other efficacy data

A capillary blood sample will be taken for immediate analysis of the participants lipid profile for assessment of efficacy. This will be performed at screening/baseline visit, day 90 visit and EOS (day 270) visit in the following:

• LDL-C calculated using Friedwald

Descriptive summaries by treatment group will be presented.

Line-Plot displaying mean and SE of change from baseline will be provided for all parameters using all available visits.

Descriptive summaries by treatment group will be presented.

Listing of all above endpoints for all available visits will be provided.

The threshold analysis on LDL-C data will be performed. Frequency and percentage of patients with secondary prevention who achieved following threshold targets at day 270 will be provided.

- <1.8 mmol/L (<70 mg/dL)
- <1.4 mmol/L (<55 mg/dL)

## 2.11 Interim analysis

There are no interim analyses planned for this study.

## 3 Sample size calculation

The primary effectiveness endpoint of the study is percent change of LDL-C from baseline. However, the sample size is driven by patient experience (CSQ-8) and patient activation (PAM); two key secondary outcomes in this trial.

The trial has been powered to detect differences equivalent to a Cohen's effect size of 0.3, approximating a 'small-to-medium' effect in conventional terms

A sample size of 300 patients per arm would be able to detect this effect size with 90% power using a one-sided significance level of 0.025 (this includes a 20% allowance for drop-out in this primary care setting).

This sample size could also detect a reduction of at least 10% change of LDL-C from baseline in the inclisiran group compared to the control group (assuming a standard deviation of 30% in the control group and 20% in the inclisiran group based on observed results from previous inclisiran studies).

The total sample size for the study will be 900 participants.

# 4 Change to protocol specified analyses

•

# 5 Appendix

5.1 Imputation rules

#### 5.1.1 Study drug

Missing/partial start date or end date of treatment will not be imputed.

#### 5.1.2 AE date imputation

#### 5.1.2.1 AE start date imputation

The following table explains the notation used in the logic matrix. Please note that completely missing start dates will not be imputed.

|                                  | Day      | Month | Year |
|----------------------------------|----------|-------|------|
| Partial Adverse Event Start Date | Not used | MON   | YYYY |
| Treatment Start Date             | Not used | TRTM  | TRTY |

The following matrix explains the logic behind the imputation.

|              | MON MISSING               | MON < TRTM                | MON = TRTM                | MON > TRTM                |
|--------------|---------------------------|---------------------------|---------------------------|---------------------------|
| YYYY MISSING | (1)                       | (1)                       | (1)                       | (1)                       |
|              | No convention             | No convention             | No convention             | No convention             |
| YYYY < TRTY  | ( 2.a )                   | (2.b)                     | (2.b)                     | (2.b)                     |
|              | Before Treatment
Start | Before Treatment
Start | Before Treatment
Start | Before Treatment
Start |
| YYYY = TRTY  | ( 4.a )                   | (4.b)                     | (4.c)                     | (4.c)                     |
|              | Uncertain                 | Before Treatment
Start | Uncertain                 | After Treatment
Start  |
| YYYY > TRTY  | ( 3.a )                   | (3.b)                     | (3.b)                     | (3.b)                     |
|              | After Treatment           | After Treatment           | After Treatment           | After Treatment           |
|              | Start                     | Start                     | Start                     | Start                     |

Before imputing AE start date, find the AE start reference date.

- If the (imputed) AE end date is complete and the (imputed) AE end date < study drug start date then AE start reference date = min(informed consent date, earliest visit date).
- Else AE start reference date = study drug start date

Impute AE start date:

- 1. If the AE start date year value is missing, the date uncertainty is too high to impute a rational date. Therefore, if the AE year value is missing, the imputed AE start date is set to NULL.
- 2. If the AE start date year value is less than the treatment start date year value, the AE started before treatment. Therefore:
  - a. If AE month is missing, the imputed AE start date is set to the mid-year point (01JULYYYY).
  - b. Else if AE month is not missing, the imputed AE start date is set to the mid-month point (15MONYYYY).
- 3. If the AE start date year value is greater than the study drug start date year value, the AE started after treatment. Therefore:
  - a. If the AE month is missing, the imputed AE start date is set to the year start point (01JANYYYY).
  - b. Else if the AE month is not missing, the imputed AE start date is set to the later of (month start point (01MONYYYY), AE start reference date + 1 day).

| Novartis | Confidential | Page 28 of 37           |
|----------|--------------|-------------------------|
| SAP      |              | Study No. CKJX839A1GB01 |

- 4. If the AE start date year value is equal to the study drug start date year value:
  - a. And the AE month is missing the imputed AE start date is set to the AE reference start date + 1 day.
  - b. Else if the AE month is less than the study drug start month, the imputed AE start date is set to the mid-month point (15MONYYYY).
  - c. Else if the AE month is equal to the study drug start date month or greater than the treatment start date month, the imputed AE start date is set to the later of (month start point (01MONYYY), AE start reference date + 1 day).

If complete (imputed) AE end date is available and the imputed AE start date is greater than the (imputed) AE end date, then imputed AE start date should be set to the (imputed) AE end date.

#### 5.1.2.2 AE end date imputaion

For the purpose of date imputation the treatment follow-up period date is defined as the last available visit date.

- 1. If the AE end date month is missing, the imputed end date should be set to the earliest of the (treatment follow up period date, 31DECYYYY, date of death).
- 2. If the AE end date day is missing, the imputed end date should be set to the earliest of the (treatment follow up period date, last day of the month, date of death).
- 3. If AE year is missing or AE is ongoing, the end date will not be imputed.
- 4. If the imputed AE end date is less than the existing AE start date then use AE start date as AE end date.

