9.1 Discontinuation and completion

9.1.1 Study treatment discontinuation and study discontinuation

Discontinuation of study treatment for a participant occurs when study treatment is stopped earlier than the protocol planned duration and can be initiated by either the participant or the investigator.

The investigator must discontinue study treatment for a given participant if he/she believes that continuation would negatively impact the participant's well-being.

Study treatment must be discontinued under the following circumstances:

• Participant decision

- Pregnancy
- Use of prohibited treatment as per recommendations in the prohibited treatment section
- Any situation in which study participation might result in a safety risk to the participant

Emergence of the following adverse events:

- Any laboratory abnormalities that in the judgment of the investigator, *taking into consideration the participant's overall status*, prevents the participant from continuing participation in the study
- Severe hypersensitivity reaction occurs, including the following: anaphylaxis associated with, fever, chills, urticaria, dyspnea, headache, myalgia, hypotension.

If discontinuation of study treatment occurs, the investigator should make a reasonable effort to understand the primary reason for the participant's premature discontinuation of study treatment and record this information.

Participants who discontinue study treatment should NOT be considered withdrawn from the study UNLESS they explicitly withdraw their consent (see Section 9.1.2 Withdrawal of Informed Consent' section). Where possible, they should be encouraged to return for the assessments indicated in the Assessment Schedule. If they fail to return for these assessments for unknown reasons, every effort (e.g. telephone, e-mail, letter) should be made to contact the participant/pre-designated contact as specified in the lost to follow-up section. This contact should preferably be done according to the study visit schedule.

Participants who discontinue treatment without withdrawing consent are effectively allowing use of their data via the electronic system for the purposes of evaluating many of the study endpoints, e.g. for the equivalent of the protocol-defined 9 month study interval.

The investigator must also contact the IRT to register the participant's discontinuation from study treatment.

Participants who discontinue study treatment or withdraw consent from the study will not be replaced.

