10.3.3 SAE reporting

To ensure participant safety, every SAE, regardless of causality, occurring after the participant has provided informed consent and until 30 days after the EOS visit must be reported to Novartis safety within 24 hours of learning of its occurrence.

Detailed instructions regarding the submission process and requirements are to be found in the investigator folder provided to each site.

All follow-up information for the SAE including information on complications, progression of the initial SAE and recurrent episodes must be reported as follow-up to the original episode within 24 hours of the investigator or delegate receiving the follow-up information. An SAE occurring at a different time interval or otherwise considered completely unrelated to a previously reported one must be reported separately as a new event.

If the SAE is not previously documented in the Investigator's Brochure or Package Insert (new occurrence) and is thought to be related to the study treatment, Chief Medical Office and Patient Safety (CMO & PS) Department associate may urgently require further information from the investigator for health authority reporting. Novartis may need to issue an Investigator Notification (IN) to inform all investigators involved in any study with the same study treatment that this SAE has been reported.

Suspected Unexpected Serious Adverse Reactions (SUSARs) will be collected and reported to the competent authorities and relevant ethics committees in accordance with EU Guidance 2011/C 172/01 or as per national regulatory requirements in participating countries.

Any SAEs experienced after the 30 day period should only be reported to Novartis Safety if the investigator suspects a causal relationship to study treatment.

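### The AE end-date rule caps partial dates at the last visit, so an SAE found in records after that visit can be given dates outside its recorded month

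*SAP*

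**What the plan says.** **End date (SAP 5.1.2.2).** The cap is defined first: "For the purpose of date imputation the treatment follow-up period date is defined as the last available visit date". For a date that lacks only its day, the rule reads: "the imputed end date should be set to the earliest of the (treatment follow up period date, last day of the month, date of death". If the month is missing too, the same rule applies with 31 December in place of the month end. Where the year is missing or the event is ongoing, nothing is imputed. Rule 4 deals with a conflict: "If the imputed AE end date is less than the existing AE start date then use AE start date as AE end date".

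**Start date (SAP 5.1.2.1).** A start in the first-dose year, but in a later month, is classed as after treatment start. Rule 4c sets it to the later of the first of that month and the reference date plus one day. The reference is consent or the earliest visit if the end precedes first dose; otherwise, "Else AE start reference date = study drug start date". The last line then overrides this result: if the imputed start is later than the end, "then imputed AE start date should be set to the (imputed) AE end date".

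**Collection window (Protocol).** Section 10.3.3 covers every SAE "occurring after the participant has provided informed consent and until 30 days after the EOS visit must be reported". Section 9.2 has participants monitored remotely over those 30 days. Section 9.1.1 adds: "Participants who discontinue treatment without withdrawing consent are effectively allowing use of their data via the electronic system", for the equivalent of the 9-month study interval. Table 8-1 has no visit after EOS.

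**The concern.** The cap and the collection window end at different times. For a completer the cap falls 30 days before SAE collection ends. For someone who stops attending but stays in the records, the gap can be many months. A partial end date from that period is therefore compared with a date that may precede the event itself. The two conflict rules then make the record internally consistent by discarding the month that was recorded.

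The SAE profile is a secondary objective, and record surveillance is the trial's chosen way to find SAEs between and after visits. The consequences to check are a wrong onset, a wrong end, the loss of an event from the treatment-emergent tables, and the merging of separate events in the registry tables. SAP 2.7.1 counts two events with the same SOC and PT as one occurrence there if the gap between them is at most one day.

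**Working it through.** The plan gives no figure to reproduce, so the check is to run its rules on example dates.

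**Inputs.** The rules are those of SAP 5.1.2.1 and 5.1.2.2. The calendar is my assumption: first dose on 1 March 2022 (Day 1). Then:
- Day 90 = 1 March + 89 days = 29 May.
- Day 270 (EOS) = 1 March + 269 days = 25 November.
- EOS + 30 days = 25 December (Day 300).

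The end date is imputed first, because the start rule uses it.

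**Distance from cap to end of collection.** It is 30 days for a completer. For a participant last seen on Day 1 and still followed in records, it is 270 − 1 = 269 days to Day 270. It is 300 − 1 = 299 days if the 30-day extension is assumed to run from Day 270.

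**Case A: completer, start and end both recorded as December 2022.**
- End = min(25 Nov, 31 Dec) = 25 Nov.
- Start = max(1 Dec, 2 Mar) = 1 Dec, which is later than the end, so start = 25 Nov.
- Both dates are now the EOS visit, in the wrong month.

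**Case B: last visit Day 1, start and end both recorded as August 2022.**
- End = min(1 Mar, 31 Aug) = 1 Mar. This is not before first dose, so the reference stays at 1 Mar.
- Start = max(1 Aug, 2 Mar) = 1 Aug, which is later than the end, so start = 1 Mar.
- The earliest possible true start is 1 Aug, so onset is at least 153 days early (1 March to 1 August).
- The SAP's own matrix classes this event as after treatment start, and rule 4c adds a day to keep it there. The override cancels both.
- SAP 2.7 restricts safety summaries to events that started after first dose or worsened later. On a date-only comparison, this event fails the first condition.

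**Case C: last visit Day 1, start 10 August 2022, end recorded as September 2022.**
- End = min(1 Mar, 30 Sep) = 1 Mar, which is before the start, so rule 4 sets end = 10 Aug.
- The imputed duration is 1 day. The record implies at least 23 days (10 August to 1 September inclusive: 22 + 1).

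**Case D: completer, start Day 260 (15 November), end recorded as December.**
- End = min(25 Nov, 31 Dec) = 25 Nov, so the event is cut to 11 days at the last visit.
- With a cap at EOS + 30 days, it would run to 25 Dec, which is 41 days.

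**Case E: registry count.** Take a last visit on Day 90 and two SAEs with the same SOC and PT, one with both dates August and one with both dates October.
- Both collapse to 29 May, so the gap is 0 days and they count as one occurrence.
- The recorded months put them at least 31 days apart (31 August to 1 October).

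**Does moving the cap to EOS + 30 days suffice?** It repairs A to E. It does not repair a related SAE with both dates recorded as February 2023, which Protocol 10.3.3 still requires to be reported:
- End = min(25 Dec 2022, 28 Feb 2023) = 25 Dec 2022.
- Start = 1 Feb 2023, which is later than the end, so start = 25 Dec 2022.

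A guard on the recorded month or year is needed for this case. The guard alone is not enough either. With only the year 2022 recorded for both dates and a last visit on Day 1, the end becomes 1 March and the start (2 March) is pulled back to it, all inside the recorded year. The later cap repairs that one (start 2 March, end 25 December). Both changes are needed.

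**The case against.** The strongest reply is that the trigger is rare and little output depends on it. Protocol Table 6-2 has AEs entered in the eCRF. Section 10.3.2 asks for start and end dates, 10.3.3 requires SAE reports and follow-up information within 24 hours, 11.2 provides for queries, and 11.3 requires full verification of SAE documentation. Nothing suggests that ConneXon delivers month-only dates. Section 8 asks for a final visit on premature discontinuation, which makes a last visit on Day 1 uncommon.

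On output, no AE-duration summary is planned, so Cases C and D change no incidence table. Case A stays treatment-emergent, because SAP 2.7 sets no end to the treatment-emergent window, and it is still counted once per participant. Case B drops out only if an onset on the first-dose date is read as not being after first dose. Case E needs repeated same-term SAEs with partial starts as well as partial ends. With complete starts, shortening the ends widens the gaps and works against merging.

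All of this stands as a limit on frequency and effect. It does not make the rule right, because an imputation rule matters only for the records that remain partial after these controls.

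A reader might infer that SAEs found after the last visit are misdated in general, or that every affected event is certainly wrong. The documents support neither. Imputation needs a missing day or month with a known year, and moving the onset needs a partial start too. Some affected events also come out right: an SAE that truly starts and ends on 10 December, with only the end recorded as December, is correctly given end = start by rule 4.

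**Conclusion.** The point holds in a narrow form. For an SAE after the last visit with a partial end date and a known year, the rule can contradict the recorded month. Onset moves back to the last visit if the start is partial too; otherwise the event becomes a one-day event. Event counts can change in two situations only: a dosed participant last seen on Day 1, with both dates partial, and the registry gap rule.

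The documents give no frequency of partial SAE dates, so the number affected cannot be estimated; it is probably small. The example dates rest on the assumed calendar, but the mechanism does not. The loss from the treatment-emergent tables also rests on a date-only comparison that excludes the first-dose date itself. This is a minor error in the written rule, worth correcting before database lock because the correction is cheap. It is no ground for doubting the main SAE tables.

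**What to change.** Make two changes to the SAP.

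1. In 5.1.2.2, replace the last available visit with the end of the participant's safety collection. That is EOS + 30 days or, without an EOS visit, the end of record follow-up, cut in either case at withdrawal of consent or death.
2. In 5.1.2.1 and 5.1.2.2, state that no imputed AE start or end date may fall outside its recorded month or year, so that neither the cap nor the start override can displace a recorded partial date.

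The cost is a sentence or two, one derived date and a small programming change. EOS + 30 days follows from the visit date. The documents do not show that a last-surveillance date is held for each participant, so the end of record follow-up for those without an EOS visit has to be defined explicitly.

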#### 5.1.3 Concomitant medication date imputation

#### 5.1.3.1 CM start date imputation

The following table explains the notation used in the logic matrix.

| 0                     | Day      | Month | Year |
|-----------------------|----------|-------|------|
| Partial CM Start Date | Not used | MON   | YYYY |
| Treatment Start Date  | Not used | TRTM  | TRTY |

The following matrix explains the logic behind the imputation.

|              | MON MISSING               | MON < TRTM                | MON = TRTM                | MON > TRTM                |
|--------------|---------------------------|---------------------------|---------------------------|---------------------------|
| YYYY MISSING | (1)                       | (1)                       | (1)                       | (1)                       |
|              | Uncertain                 | Uncertain                 | Uncertain                 | Uncertain                 |
| YYYY < TRTY  | ( 2.a )                   | (2.b)                     | (2.b)                     | (2.b)                     |
|              | Before Treatment
Start | Before Treatment
Start | Before Treatment
Start | Before Treatment
Start |
| YYYY = TRTY  | (4.a)                     | (4.b)                     | (4.a)                     | (4.c)                     |
|              | Uncertain                 | Before Treatment
Start | Uncertain                 | After Treatment
Start  |
| YYYY > TRTY  | ( 3.a )                   | (3.b)                     | (3.b)                     | (3.b)                     |

| MON MISSING     | MON < TRTM      | MON = TRTM      | MON > TRTM      |
|-----------------|-----------------|-----------------|-----------------|
| After Treatment | After Treatment | After Treatment | After Treatment |
| Start           | Start           | Start           | Start           |

- 1. If the CM start date year value is missing, the imputed CM start date is set to one day prior to treatment start date.
- 2. If the CM start date year value is less than the investigational study treatment start date year value, the CM started before treatment. Therefore:
  - a. If the CM month is missing, the imputed CM start date is set to the mid –year point (01JULYYYY).
  - b. Else if the CM month is not missing, the imputed CM start date is set to the mid-month point (15MONYYYY).
- 3. If the CM start date year value is greater than the investigational study treatment start date year value, the CM started after treatment. Therefore:
  - a. If the CM month is missing, the imputed CM start date is set to the year start point (01JANYYYY).
  - b. Else if the CM month is not missing, the imputed CM start date is set to the month start point (01MONYYYY).
- 4. If the CM start date year value is equal to the investigational study treatment start date year value:
  - a. And the CM month is missing or the CM month is equal to the treatment start date month, then the imputed CM start date is set to one day prior to treatment start date.
  - b. Else if the CM month is less than the treatment start date month, the imputed CM start date is set to the mid-month point (15MONYYYY).
  - c. Else if the CM month is greater than the treatment start date month, the imputed CM start date is set to the month start point (01MONYYYY).

If complete (imputed) CM end date is available and the imputed CM start date is greater than the (imputed) CM end date, then imputed CM start date should be set to the (imputed) CM end date.

